5.5.1.1 Abnormal Laboratory Findings

Any abnormal laboratory test result (e.g. hematology, clinical chemistry, or urinalysis) or other safety assessment (e.g., ECGs, radiolographic scans, vital signs measurements, physical examination), including those that worsen from baseline, that is considered to be clinically significant in the medical and scientific judgment of the investigator and not related to underlying disease, is to be reported as an (S)AE.

Any clinically significant abnormal laboratory finding or other abnormal safety assessment which is associated with the underlying disease does not require reporting as an (S)AE, unless judged by the investigator to be more severe than expected for the subject's condition.

Repeating an abnormal laboratory test or other safety assessment, in the absence of any of the above criteria, does not constitute an AE. Any abnormal test result that is determined to be an error does not require reporting as an AE.

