5.5 Adverse Events and Other Safety Aspects

5.5.1 Definition of Adverse Events

An AE is any untoward medical occurrence in a subject, temporally associated with the use of a medicinal product, whether or not considered related to the medicinal product. An AE can therefore be any unfavorable and unintended sign (including an abnormal laboratory finding), symptom, or disease (new or exacerbated) temporally associated with the use of a medicinal product.

In order to identify any events that may be associated with study procedures and could lead to a change in the conduct of the study, Astellas collects AEs even if the subject has not received study drug treatment. AE collection begins after the signing of the informed consent and will be collected until subject is determined to be ineligible for study entry, or initiation of new therapy for prostate cancer including commercial enzalutamide, or 30 days after the last dose of study drug, whichever occurs first.

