5.5.1.3 Disease Progression and Study Endpoints

Under this protocol, the following event(s) will not be considered as an(S)AE:

- Disease Progression: events including defined study endpoints that are clearly consistent with the expected pattern of progression of the underlying disease are not to be recorded as AEs. These data will be captured as efficacy assessment data as outlined in Section 5.3.1. If there is any uncertainty as to whether an event is due to anticipated disease progression and/or if there is evidence suggesting a causal relationship between the study drug and the event, it should be reported as an (S)AE.
- Pre-planned and elective hospitalizations or procedures for diagnostic, therapeutic, or surgical procedures for a pre-existing condition that did not worsen during the course of the clinical trial. These procedures are collected per the eCRFs Completion Guidelines.

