Thrombocytopenia Musculoskeletal Events	 PTs of 'Thrombocytopenia', 'Platelet Count Decreased'. PTs of 'Back Pain', 'Arthralgia', 'Myalgia', 'Musculoskeletal Pain', 'Pain In Extremity', 'Musculoskeletal Stiffness', 'Muscular Weakness','Muscle Spasms'. 	
Severe Cutaneous Adverse Reactions (SCAR)	Narrow SMQ of 'Severe Cutaneous Adverse Reactions'.	

AESI (Adverse Events of Special Interest) are defined as below.

AESI Category	Selection based on MedDRA 26.0	
Angioedema	Narrow SMQ of 'Angioedema'.	
	PTs of 'Butterfly rash', 'Exfoliative rash', 'Eyelid rash',	
	'Genital rash', 'Heliotrope rash', 'Mucocutaneous rash',	
	'Nodular rash', 'Paraneoplastic rash', 'Penile rash', 'Perineal	
	rash', 'Rash', 'Rash erythematous', 'Rash follicular', 'Rash	
Rash	macular', 'Rash maculo-papular', 'Rash maculovesicular',	
Kasii	'Rash morbiliform', 'Rash neonatal', Rash papular', 'Rash	
	papulosquamus', 'Rash pruritic', 'Rash pustular', 'Rash	
	rubelliform', 'Rash scarlataniniform',' Rash vesicular', 'Septic	
	rash', 'Systemic lupus erythematosus rash', 'Vasculitic rash',	
	'Viral rash', 'Vulvovaginal rash'.	
	Narrow SMQ of 'Hepatic Failure, Fibrosis And Cirrhosis	
Δ	And Other Liver Damage Related Conditions', 'Hepatitis,	
Hepatic Disorder	Non-Infectious' And 'Liver Related Investigations, Signs	
	And Symptoms'.	

SMQ: Standardized MedDRA Query, HLT: High Level Term, HLGT: High Level Group Term.

[1] Broad includes either broad or narrow.

[2] AE terms identified as second primary malignancies according to the search criteria undergo review to confirm.

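### Protocol 5.5.1.1 lacks the uncertain-cause override found in 5.5.1.3, so laboratory findings of mixed cause can be missing from the TEAE and AESI counts

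*Protocol*

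**What the plan says.** Protocol 5.5.1 defines an adverse event without regard to cause, "whether or not considered related to the medicinal product", and brings laboratory results into the definition: "An AE can therefore be any unfavorable and unintended sign (including an abnormal laboratory finding".

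Protocol 5.5.1.1 then sets the rule for test results. Its first paragraph creates a duty to report a finding that the investigator considers clinically significant "and not related to underlying disease, is to be reported as an (S)AE". Its second paragraph releases a clinically significant finding "which is associated with the underlying disease does not require reporting as an (S)AE, unless judged by the investigator to be more severe than expected". Greater-than-expected severity is the only way back in.

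Protocol 5.5.1.3 deals with disease progression. It keeps out of the AE record those events that are "clearly consistent with the expected pattern of progression of the underlying disease". It restores reporting when there is any doubt that progression is the explanation, and also says that "if there is evidence suggesting a causal relationship between the study drug and the event, it should be reported as an (S)AE".

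SAP 6.2 defines the adverse events of special interest (AESIs) by MedDRA terms. Thrombocytopenia, for instance, is "PTs of 'Thrombocytopenia', 'Platelet Count Decreased". Neutrophil count decreased, renal disorder and hepatic disorder are defined in the same way. SAP 7.5.1.3 counts patients with treatment-emergent adverse events (TEAEs) in those categories. Separately, SAP 7.5.2 summarises all laboratory values for the safety set, whether or not an AE was recorded.

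**The concern.** The frequency and severity of adverse events is a primary endpoint, and neutrophil count decreased is among the important identified risks in Protocol 1.4. In this population the cancer itself can explain some abnormal results. Appendix 12.2 uses a different transaminase threshold for subjects with liver metastases, and the SAP's baseline table lists bone marrow and liver as metastatic sites.

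When disease and drug are both plausible, 5.5.1.1 has the investigator settle the question before an AE record exists. A finding exempted at that point gets no seriousness, severity or causality assessment. It also bypasses the SAP's conservative rule that a missing causality assessment counts as drug-related, because there is no record to which the rule can apply. The study is open-label and single-arm, so no control group is subject to the same filter, and there is no data monitoring committee.

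**Working it through.** The plan gives no figure to reproduce, since the sample size of 50 is stated not to rest on a power calculation. The check is mainly a comparison of texts.

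**Step 1. Run three kinds of clinically significant laboratory finding through the two rules.**

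| Investigator's view of the cause | Under 5.5.1.1 | If the 5.5.1.3 override applied |
|---|---|---|
| Drug, or another cause that is not the cancer | Reportable (first paragraph) | Reportable |
| Cancer alone, of expected severity | Exempt | Not recorded as an AE |
| Cancer plus a possible drug effect, or uncertain | Does not clearly meet the first paragraph's unrelated-to-disease condition; can be exempted under the second unless worse than expected | Reportable |

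The rules differ only in the third row. That row is the whole of the gap.

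**Step 2. See where a third-row finding still appears.**
- SAP 7.5.1.2 and 7.5.1.3 (TEAE and AESI tables): absent, because these count coded AE terms.
- SAP 7.5.2.1 (all laboratory tests): present, in descriptive statistics, plots and low/normal/high shift tables. A shift to low does not separate a slightly low count from a grade 3 or 4 count.
- SAP 7.5.2.2 (threshold tables): present for liver tests only, as multiples of the upper limit of normal. There is no such table for neutrophils, platelets or creatinine.
- Protocol 5.5.1.2 (potential drug-induced liver injury): must be reported, but only when no other cause is present. It does not secure the subject with liver metastases.

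**Step 3. The weight of one missed subject (n = 50, planned).**
- 1/50 = 2 percentage points.
- The cut-off for common TEAEs in SAP 7.5.1.2 is 5%. Since 0.05 × 50 = 2.5, a term needs 3 subjects to be listed.
- 3/50 = 6.0% (exact 95% interval 1.3% to 16.5%). One subject fewer gives 2/50 = 4.0% (0.5% to 13.7%), and the term drops off the list.

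The intervals overlap heavily, so sampling error at this size exceeds the loss of one case. The loss differs in kind: it always lowers the count, and no interval reflects it.

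**Step 4. Sensitivity, with assumed inputs.** Let p be the true proportion of subjects with one given term and m the share of those cases left unreported. Neither is in the documents. The number reported is then binomial with n = 50 and probability p(1 − m).

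| p | m | Expected reported, 50p(1 − m) | Chance of at least 3 reported |
|---|---|---|---|
| 5% | 0% | 2.5 | 0.46 |
| 5% | 10% | 2.25 | 0.39 |
| 5% | 25% | 1.88 | 0.29 |
| 5% | 50% | 1.25 | 0.13 |
| 10% | 0% | 5.0 | 0.89 |
| 10% | 10% | 4.5 | 0.84 |
| 10% | 25% | 3.75 | 0.73 |
| 10% | 50% | 2.5 | 0.46 |

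Only mixed-cause cases are exposed to the exemption, so the larger values of m would require most cases of a term to be of that kind. The table shows how sensitive a count is at n = 50. It does not estimate what will happen.

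**The case against.** The strongest reply is that nothing here conflicts. Section 5.5.1.1 grants a permission and 5.5.1.3 imposes a duty. Both sit under 5.5.1, and read together the duty prevails. A reader might nevertheless infer that the two sections flatly contradict each other. The documents do not support that, because one governs test findings and the other progression events. The same distinction limits the reply: the duty does not name an isolated laboratory value, so an investigator who applies 5.5.1.1 alone is following the text.

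A reader might also infer that the safety evidence itself is lost. It is not. Laboratory tests are a primary endpoint in their own right and are tabulated for every treated subject. Protocol 5.4.3 has the investigator document the clinical significance of out-of-range results. Liver findings have further cover: Appendix 12.2 calls for a liver abnormality form for confirmed abnormalities and has symptoms and new illnesses recorded as AEs. What remains exposed is the AE and AESI count, chiefly for neutrophils, platelets and creatinine.

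Vital signs are formally in scope, since 5.5.1.1 extends to "other safety assessment (e.g., ECGs, radiolographic scans, vital signs measurements, physical examination". A reader might infer that hypertension is undercounted by the same route. The documents list hypertension as an identified risk of the drug and nowhere present it as a sign of the cancer, so that inference has no support.

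Finally, counting disease-driven cytopenias with no comparator could make the drug look worse, and an investigator who blames the disease would probably answer no on causality anyway. Both points are fair for the drug-related tables. They do not excuse a gap in the all-cause TEAE tables, which 5.5.1 intends to be independent of cause.

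**Conclusion.** The concern holds in a limited form. By following 5.5.1.1 as written, an investigator can leave a clinically significant laboratory finding of mixed or uncertain cause out of the AE record, and so out of the TEAE and AESI counts. Findings ascribed to the drug are already reportable, and the laboratory values themselves are retained.

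The size is 2 percentage points per missed subject, assuming 50 treated subjects. One subject is enough to move a term from 6% to 4%, across the common-TEAE cut-off. How many subjects would be affected, if any, cannot be derived from the documents. A reader might be tempted to pool such findings into one AESI rate and show it falling steeply; that would rest on invented inputs and on merging categories that the SAP reports separately.

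The existing tables do not fully make up for the missing records, because shift categories are not CTCAE grades and only liver tests have threshold counts. The change is worth making because it is cheap and the protocol already has the wording.

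**What to change.** 1. **Protocol 5.5.1.1.** Add the 5.5.1.3 override: a clinically significant abnormal finding is reported as an (S)AE if there is any uncertainty that the disease explains it, and/or evidence suggesting that study drug contributed. In both paragraphs, limit the exemption to findings explained by the disease alone. Align the eCRF completion guideline.
2. **SAP 7.5.2.** Add CTCAE-graded tables for neutrophils, platelets and creatinine from the central laboratory data, set beside the matching AESI counts, and list subjects who have a graded abnormality but no corresponding AE term. This needs no new data: Protocol Table 2 already includes the white cell differential, platelet count and creatinine.

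**Cost.** The first change affects the evaluation of safety, so under Protocol 8.3.3 it needs IRB/IEC approval before use. It will bring in a few more laboratory AEs. If made mid-study, it leaves two reporting rules in one database, which the CSR should note with the date of the change. The AESI analyses entered only with SAP version 3.0 of 26 February 2024, so the amendment may come late for much of the data. The second change avoids the mixed-rule problem, costs a few programmed outputs, and can be made at any time before the SAP is finalised for hard lock. If only one change is feasible, it still shows how far the AESI counts and the laboratory data differ.

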5.5.1.2 Potential Cases of Drug-Induced Liver Injury

Refer to [Appendix 12.2 Liver Safety Monitoring and Assessment] for detailed instructions on Drug Induced Liver Injury (DILI). Abnormal values in aspartate transaminase (AST) and/or alanine transaminase (ALT) concurrent or with abnormal elevations in total bilirubin that meet the criteria outlined in [Appendix 12.2 Liver Safety Monitoring and Assessment], in the absence of other causes of liver injury, are considered potential cases of drug-induced liver injury (potential Hy's Law cases) and are always to be considered important medical events and reported per [Section 5.5.5 Reporting of Serious Adverse Events].

5.5.1.3 Disease Progression and Study Endpoints

Under this protocol, the following event(s) will not be considered as an(S)AE:

- Disease Progression: events including defined study endpoints that are clearly consistent with the expected pattern of progression of the underlying disease are not to be recorded as AEs. These data will be captured as efficacy assessment data as outlined in Section 5.3.1. If there is any uncertainty as to whether an event is due to anticipated disease progression and/or if there is evidence suggesting a causal relationship between the study drug and the event, it should be reported as an (S)AE.
- Pre-planned and elective hospitalizations or procedures for diagnostic, therapeutic, or surgical procedures for a pre-existing condition that did not worsen during the course of the clinical trial. These procedures are collected per the eCRFs Completion Guidelines.

5.5.2 Definition of Serious Adverse Events (SAEs)

An AE is considered "serious" if, in the view of either the investigator or sponsor, it results in any of the following outcomes:

- Results in death
- Is life-threatening (an AE is considered "life-threatening" if, in the view of either the investigator or sponsor, its occurrence places the subject at immediate risk of death. It does not include an AE that, had it occurred in a more severe form, might have caused death)
- Results in persistent or significant disability/incapacity or substantial disruption of the ability to conduct normal life functions
- Results in congenital anomaly, or birth defect
- Requires inpatient hospitalization (except for planned procedures as allowed per study) or leads to prolongation of hospitalization (except if prolongation of planned hospitalization is

not caused by an AE). Hospitalization for treatment/observation/examination caused by AE is to be considered as serious.)

• Other medically important events (defined in paragraph below)

Medical and scientific judgment should be exercised in deciding whether expedited reporting is appropriate in other situations, such as important medical events that may not be immediately life-threatening or result in death or hospitalization but may jeopardize the subject or may require intervention to prevent 1 of the other outcomes listed in the definition above. These events, including those that may result in disability/incapacity, usually are considered serious. Examples of such events are intensive treatment in an emergency room or at home for allergic bronchospasm; blood dyscrasias or convulsions that do not result in hospitalization; or development of drug dependency or drug abuse.

The sponsor has a list of events that they classify as "always serious" events. If an AE is reported that is considered to be an event per this classification as "always serious", additional information on the event may be requested.

5.5.3 Criteria for Causal Relationship to Study Drug

The investigator is obligated to assess the relationship between the study drug and each occurrence of each (S)AE. The investigator will use clinical judgment to determine the relationship. The investigator should also use the Investigator's Brochure (IB). The investigator is requested to provide an explanation for the causality assessment for each SAE (Serious adverse event) and must document this on the SAE worksheet. The causality assessment is one of the criteria used when determining regulatory reporting requirements. The investigator may revise his/her assessment of causality in light of new information regarding the SAE and shall send an SAE follow-up report and update the eCRF (Electronic case report form) with the new information and updated causality assessment. Following a review of the relevant data, the causal relationship between the study drug and each (S)AE will be assessed by answering 'yes' or 'no' to the question "Do you consider that there is a reasonable possibility that the event may have been caused by the study drug". When making an assessment of causality, the following factors are to be considered when deciding if there is evidence and/or arguments to suggest there is a 'reasonable possibility' that an (S)AE may have been caused by the study drug (rather than a relationship cannot be ruled out) or if there is evidence to reasonably deny a causal relationship:

- Plausible temporal relationship between exposure to the study drug and (S)AE onset and/or resolution. Has the subject actually received the study drug? Did the (S)AE occur in a reasonable temporal relationship to the administration of the study drug?
- Plausibility; i.e., could the event been caused by the study drug? Consider biologic and/or pharmacologic mechanism, half-life, literature evidence, drug class, preclinical and clinical study data, etc.
- Dechallenge/Dose reduction/Rechallenge:

- Did the (S)AE resolve or improve after stopping or reducing the dose of the suspect drug? Also consider the impact of treatment for the event when evaluating a dechallenge experience.
- Did the (S)AE reoccur if the suspected drug was reintroduced after having been stopped?
- Laboratory or other test results; a specific lab investigation supports the assessment of the relationship between the (S)AE and the study drug (e.g., based on values pre-, during and post-treatment)
- Available alternative explanations independent of study drug exposure; such as other concomitant drugs, past medical history, concurrent or underlying disease, risk factors including medical and family history, season, location, etc. and strength of the alternative explanation

There may be situations in which an SAE has occurred and the investigator has minimal information to include in the initial report to delegated CRO. However, it is very important that the investigator always make an assessment of causality for every event before the initial transmission of the SAE data to delegated CRO. With limited or insufficient information about the event to make an informed judgment and in absence of any indication or evidence to establish a causal relationship, a causality assessment of 'no' is to be considered. In such instance, the investigator is expected to obtain additional information regarding the event as soon as possible and to re-evaluate the causality upon receipt of additional information.

5.5.4 Criteria for Defining the Severity of an Adverse Event

AEs, including abnormal clinical laboratory values, will be graded using the CTCAE guidelines (Version 4.03). The items that are not stipulated in the NCI-CTCAE Version 4.03 will be assessed according to the criteria below and entered into the eCRF.

Grade	Assessment Standard
1-Mild	Asymptomatic or mild symptoms, clinical or diagnostic observations noted; intervention not indicated.
2-Moderate	Local or noninvasive intervention indicated.
3-Severe	Medically significant but not immediately life threatening, hospitalization or prolonged hospitalization.
4-Life Threatening	Life threatening consequences, urgent intervention indicated
5-Death	Death related to AE

5.5.5 Reporting of Serious Adverse Events (SAEs)

The collection of AEs and the expedited reporting of SAEs will start following receipt of the informed consent and will continue to safety follow-up visit.

In the case of a SAE, the investigator must contact delegated CRO by fax or email immediately (within 24 hours of awareness).

The investigator must complete and submit a SAE worksheet containing all information that is required by local and/or regional regulations to delegated CRO by email or fax immediately (within 24 hours of awareness).

For contact details, see [Section II Contact Details of Key Sponsor's Personnel]. Fax or email the SAE Worksheet to:

IQVIA RDS East Asia Pte. Ltd.

Lifecycle Safety

[contact] Email: [contact]

If there are any questions, or if clarification is needed regarding the SAE, please contact the sponsor's Medical Monitor/Study Physician or his/her designee [Section II Contact Details of Key Sponsor's Personnel].

Follow-up information for the event should be sent promptly (within 7 days of the initial notification).

Full details of the SAE should be recorded on the medical records, SAE Worksheet and on the (e)CRF.

The following minimum information is required:

- International Study Number (ISN)/Study number,
- Subject number, sex and age,
- The date of report,
- A description of the SAE (event, seriousness criteria),
- Causal relationship to the study drug (including reason), and
- The drug provided (if any)

The sponsor or sponsor's designee will submit expedited safety reports (e.g., IND Safety Reports, CIOMS-I) to Competent Authorities (CA) and concerned Ethics Committee (cEC) per current local regulations, and will inform the investigators of such regulatory reports as required. Investigators must submit safety reports as required by their IRB/local IEC within timelines set by regional regulations (e.g., EU, FDA) where required. Documentation of the submission to and receipt by the IRB/ local IEC of expedited safety reports should be retained by the site.

The sponsor or designee will notify all investigators responsible for ongoing clinical studies with the study drug of all SAEs which require submission per local requirements.

The heads of the study sites/investigators should provide written documentation of IRB/IEC notification for each report to the sponsor.

The investigator may contact the sponsor's Medical Monitor/Study Physician for any other problem related to the safety, welfare, or rights of the subject.

